8.3.2 Handling of Missing Data for the Primary Efficacy Endpoint

For primary analysis, the missing data will be handled using a MMRM model with the missing at random (MAR) assumption, in which both missingness of data and the correlation of the repeated measurements will be considered.

8.3.3 Primary Efficacy Analysis

Primary efficacy endpoint (overall composite driving performance Z score approximately 1 hour after study intervention instillation) will be analyzed using a linear mixed-effects model with repeated measures (MMRM).

The model will use overall composite driving performance Z score approximately 1 hour after study intervention instillation as dependent variable, include study intervention group (AGN-190584, vehicle), study intervention sequence (Sequence 1: AGN-190584 followed by vehicle, Sequence 2: vehicle followed by AGN-190584), and study period (Period 1, Period 2) as fixed effects and participant nested within sequence of testing as a random effect. The covariance structure to model the within-participant correlation error structure will be unstructured. If the unstructured covariance matrix results in a lack of convergence, compound symmetry covariance structure will be used. The Kenward-Roger method will be used to estimate the denominator degrees of freedom.

The least-square (LS) mean and 95% CI will be provided for each study intervention (AGN-190584, or vehicle) in overall composite driving performance driving Z score.

The comparison between the two study interventions (AGN-190584 vs. vehicle) will be performed by providing LS mean and 95% CI for the between-group difference in the overall composite driving performance Z score. Noninferiority of AGN-190584 will be concluded if the lower bound of the 95% CI of the least square mean difference between AGN-190584 and vehicle is greater than -0.25.

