#### **9.4.1.2. Primary Analyses**

Overall composite driving Z score will be analyzed using MMRM. The model will include study intervention group, study intervention sequence, and study period as fixed effects and participant nested within sequence of testing as a random effect. The within-participant correlation error structure is unstructured. Noninferiority of AGN-190584 will be concluded if the lower bound of the 95% confidence interval of the least square mean difference between AGN-190584 and vehicle is greater than -0.25.

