2.4 Sample Size Determination

The sample size calculation is based on the primary efficacy endpoint. Assuming no difference between treatment groups and variance of 0.11, approximately 40 participants will be required to obtain 90% power for a 1-sided noninferiority test with type 1 error of 0.025 and noninferiority margin of -0.25 units in mean overall composite driving performance Z score. Therefore, approximately 54 participants will be enrolled to achieve 40 participants completing the study assuming an anticipated dropout rate of 25% or less.

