8.0 Efficacy Analyses

8.1 General Considerations

- The primary analysis will be performed after the database is locked and randomization schedule is released.
- Efficacy endpoints will be analyzed using the ITT population. The 95% confidence intervals will be provided for the primary endpoint.

- Baseline for efficacy is defined as the last nonmissing efficacy assessment before the first dose of study intervention in each period or randomization if no study drug is given when applicable.
- Continuous variables will be summarized by number of participants with observed values (n), mean, standard deviation, median, 1st and 3rd quartiles, minimum, and maximum.
- Categorical variables will be summarized by number of participants with observed values (n), frequency counts (n1) and percent of participants with observed values.

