8.3 Primary Efficacy Endpoint and Analyses

8.3.1 Primary Efficacy Endpoint

The night-driving evaluation will be performed approximately 1 hour following study intervention instillation at both driving visits.

The overall composite driving performance Z score for a participant is calculated using the average of Z scores for the following component driving measures: percent hazards hit, percent sign recognition and recognition distance, pedestrian recognition distance, lap duration and percent of time outside of the lane (lane-keeping).

A participant's Z score for a given component driving measure is calculated using the mean and standard deviation from the pooled treatment data. Since a lower percent of hazards hit, lower percentage of time outside of the lane and a shorter lap duration is indicative of better performance, the Z scores of these three components are reversed (e.g., $-1 \times Z$ score) before computing the overall driving Z score.

The primary efficacy endpoint is overall composite driving performance Z score approximately 1 hour after study intervention instillation.

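### Does fitting both a random participant effect and an unstructured error matrix to two scores per participant undermine the primary analysis?

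*SAP*

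**What the plan says.** SAP 8.3.3 fits the composite driving Z score with fixed effects for treatment, sequence and period, and with "participant nested within sequence of testing as a random effect". It then says: "The covariance structure to model the within-participant correlation error structure will be unstructured". The fallback is: "If the unstructured covariance matrix results in a lack of convergence, compound symmetry covariance structure will be used". It adds: "The Kenward-Roger method will be used to estimate the denominator degrees of freedom".

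Protocol 9.4.1.2 has the same random term and says "The within-participant correlation error structure is unstructured", with no fallback.

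SAP 8.3.1 fixes the number of scores: "The night-driving evaluation will be performed approximately 1 hour following study intervention instillation at both driving visits". That is one composite score at each of Visits 3 and 5, so at most two per participant. SAP 2.4 plans for incomplete pairs, "assuming an anticipated dropout rate of 25% or less". On timing, SAP 8.1 says: "The primary analysis will be performed after the database is locked and randomization schedule is released".

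**The concern.** A 2x2 within-participant covariance matrix has three distinct elements: two variances and a covariance. An unstructured error matrix uses all three, so a random participant effect on top makes four parameters for three elements. Under the fallback, with the random effect kept, there are three parameters for two elements. In both cases the likelihood is flat in one direction and its Hessian is singular whatever the data.

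The worry is procedural. The SAP does not say whether a singularity warning counts as non-convergence. One programmer might keep the unstructured fit and another might switch to compound symmetry, and with incomplete pairs these give different answers. If the choice arose only at the final run, it would be made with treatment assignments known, in a trial with a single confirmatory test.

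**Working it through.** **Inputs.** From SAP 2.4: variance 0.11, margin -0.25, one-sided 0.025, 90% power, 40 completers, 54 enrolled. From SAP 2.3: 1:1 allocation, so 20 completers per sequence. Assumed, because the documents give no covariance matrix: the variances named below, and dropout unrelated to outcome.

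**1. The plan's own figure.** Read 0.11 as the within-participant variance of one score (the documents do not label it). A paired difference then has variance 2 × 0.11 = 0.22. The normal approximation gives (1.960 + 1.282)² × 0.22 / 0.25² = 37.0. The t-based version with N − 2 df gives N = 40, power 90.7%. Dropout: 40 / 0.75 = 53.3, rounded up to 54. The covariance wording does not enter this calculation.

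**2. Where the redundancy sits.** Let b be the participant variance, J the all-ones 2x2 matrix and R the error matrix. The data inform only V = bJ + R. For any constant c, (b + c)J + (R − cJ) = V, so b and R cannot be separated, but V can be estimated. Setting b = 0 gives every V that the unstructured matrix allows; the same holds for compound symmetry. The fitted V, and all that depends on it, is therefore the same with or without the random term.

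**3. Numerical confirmation.** Eigenvalues of the REML information at V = [[0.33, 0.22], [0.22, 0.33]], 20 pairs per sequence:

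| Model | Parameters | Rank | Eigenvalues |
|---|---|---|---|
| Unstructured + random | 4 | 3 | 0, 314, 333, 2368 |
| Unstructured only | 3 | 3 | 83, 314, 2366 |
| Compound symmetry + random | 3 | 2 | 0, 475, 1660 |
| Random only | 2 | 2 | 240, 1644 |

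In a simulated data set of 40 complete pairs, four starting values for the unstructured-plus-random model all reached −2 REML log-likelihood −112.1076, with participant variance anywhere from 0.013 to 0.057. The estimate (−0.0407), SE (0.0460) and df (38.0) equalled those of the unstructured model alone. In 2,400 simulated trials, adding the random term changed the estimate, SE, lower bound and df by less than 1e-12.

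**4. A switch with complete pairs.** Intercept, treatment, sequence and period are four parameters for four cell means, so the estimate does not depend on V. Its variance at the V above is (1/4)(0.22/20 + 0.22/20) = 0.0055, so SE = 0.07416, with 40 − 2 = 38 df. Unstructured and compound symmetry agree exactly.

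**5. A switch with incomplete pairs.** Upper case: 54 − 40 = 14 participants have Period 1 only, meaning every loss falls after Visit 3.

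- At the same V: unstructured SE 0.07297, df 40.54; compound symmetry SE 0.07277, df 41.45.
- One data set simulated with unequal variances (0.08 and 0.16, covariance 0.05): unstructured −0.0470, SE 0.0532, df 38.8; compound symmetry −0.0506, SE 0.0501, df 43.7. Lower bounds: −0.0470 − 2.023 × 0.0532 = −0.155 and −0.0506 − 2.016 × 0.0501 = −0.152. They differ by about 0.003.
- 400 trials per pattern, participant variance 0.14, Period 1 residual variance 0.11. Absolute shift in the lower bound:

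| Period 2 residual variance | Median | 95th percentile | Maximum |
|---|---|---|---|
| 0.11 | 0.0018 | 0.0096 | 0.0203 |
| 0.055 | 0.0027 | 0.0119 | 0.0266 |
| 0.22 | 0.0051 | 0.0172 | 0.0298 |

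- The df moved by −6.5 to +6.3. From 40.5 df the critical value goes from 2.020 to 2.032 or 2.012; at SE 0.073 that is at most 0.012 × 0.073 = 0.0009.

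**6. Effect on the decision, same 14 incomplete.** With a true difference of 0 and 1,500 trials per pattern (fixed critical value 2.02), the two structures disagreed on noninferiority in 0.4%, 0.3% and 2.0% of trials; the largest shifts were 0.026 to 0.045. The false noninferiority rates, unstructured against compound symmetry, were 0.016 against 0.015, 0.026 against 0.023 and 0.032 against 0.033 across three variance patterns. Where the rate departs from 0.025, it does so under both structures.

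**The case for a change.** The strongest case for a change is that a single confirmatory test should leave no choice of covariance model open, and that one sentence would settle it. It can be added that the text does not say which term is meant: a random effect alone amounts to compound symmetry (for non-negative correlation), an error matrix alone is unstructured, and these differ once pairs are incomplete.

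The parameter count stands. The rest carries less weight than it seems.

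- **Which model is meant.** The SAP names the unstructured matrix as primary. Fitting both terms literally, or the matrix alone, gives the same result. A random effect alone would contradict the stated structure.
- **The trigger.** A singular Hessian at a maximum that has been reached means two components cannot be separated. It does not mean that the maximum was not found. If the participant variance is held at its zero bound, what remains is the full-rank unstructured model. No failed fit was seen, but the check did not use the software the SAP names, so how often that would give a warning is unknown.
- **The timing.** SAP 8.1 says when the primary analysis is run, not when the program is written. Protocol section 9 requires a final SAP before lock and unmasking. Since the redundancy appears with any data, a trial run on masked data would expose it beforehand.

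**Conclusion.** The concern is right about the algebra and does not call for a change. Both the primary specification and its fallback, read literally, carry one covariance parameter too many, but the superfluous parameter has no bearing on the treatment difference, its confidence bound or the noninferiority decision.

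Harm would need a warning, a reading of that warning as non-convergence, a good number of incomplete pairs and a result close to −0.25, all together. In the assumed upper case the typical cost is a bound shift of 0.002 to 0.005, about 1% to 2% of the margin. The largest single-trial shift was 0.045, and the false noninferiority rate differed by at most 0.003 between structures.

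The redundancy result needs no assumption about the variances. The sizes in the incomplete-pair case rest on the assumed variances, on all 14 losses falling after Visit 3 and on dropout unrelated to outcome. An analyst who fits the unstructured matrix alone, or keeps the random term and reads the fitted total covariance, follows the plan and reports the same primary result.

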8.3.4 Additional Analyses of the Primary Efficacy Endpoint

The primary endpoint will also be summarized by descriptive statistics. The observed data will be used, and no imputation will be performed.

8.4 Other Efficacy Analyses

The other effectiveness analyses will be performed using the ITT population for all variables listed in [Table 8-1](#)

The continuous efficacy endpoints will be summarized by descriptive statistics. The number and percentage of participants reporting each response will be provided for the 12 questions in the night-driving experience questionnaire. The denominator will be the number of the participants with a non-missing response for the specific question. The results will be presented by study intervention group. The results for “AGN-190584” group will be based on Period 1 data for study intervention sequence “AGN-190584 followed by vehicle”, and Period 2 data for study intervention sequence “vehicle followed by AGN-190584”. The results for “vehicle” group will be based on Period 2 data for study intervention sequence “AGN-190584 followed by vehicle”, and Period 1 data for study intervention sequence “vehicle followed by AGN-190584”.

The other efficacy analysis results will be deemed supportive. No hypotheses will be tested on the other efficacy endpoints, and no multiplicity adjustment will be performed.

Table 8-1 Other Effectiveness Analyses

Endpoint	Description	Derivation	Methodology
Hazard avoidance	Percentage of hazards hit for each participant	Calculated from the reported total number of hazards and the number of hazards hit.	Continuous descriptive statistics
Sign recognition	Percentage of sign recognition for each participant	Calculated from the reported total number of signs and the number of signs correctly identified	Continuous descriptive statistics
Sign recognition distance	Recognition distance in meters to one specific sign	Reported distance	Continuous descriptive statistics
Lane-keeping	Percentage of time outside of the lane (lane-keeping)	Calculated post-testing from the reported total driving time and reported time outside of lane. Lane crossings where the participant is responding to a hazard on the road are not included.	Continuous descriptive statistics
Pedestrian recognition distance	Distance for pedestrian recognition	Reported distance	Continuous descriptive statistics
Driving time	The time to complete the road course	Reported time (min, sec) converted to seconds	Continuous descriptive statistics
Pupil diameter	Measured before dosing, after dosing at driving test visit in each eye	Reported value	Continuous descriptive statistics
Halometer	The area of the halo surrounding the LED glare source	Reported value	Continuous descriptive statistics
Night-driving experience questionnaire	12 questions to evaluate the participants' night driving experience	Reported responses to each question	Ordinal descriptive statistics and response frequencies

8.5 Efficacy Subgroup Analyses

No efficacy subgroup analyses will be performed for this study.

9.0 Safety Analyses

9.1 General Considerations

- The safety endpoints will be analyzed with descriptive statistics using the safety population.
- The safety results will be presented by study intervention group.
- The results for “AGN-190584” group will be based on Period 1 data for study intervention sequence “AGN-190584 followed by vehicle”, and Period 2 data for study intervention sequence “vehicle followed by AGN-190584”.
- The results for “vehicle” group will be based on Period 2 data for study intervention sequence “AGN-190584 followed by vehicle”, and Period 1 data for study intervention sequence “vehicle followed by AGN-190584”.
- For each study period, the baseline for safety parameters will be the last assessment prior to the first administration of study intervention in the period unless specified otherwise.
- For each study period, the change from baseline values will be computed as the postbaseline value minus the baseline value (defined above) for that study period.
- Continuous variables will be summarized by number of participants with observed values (n), mean, standard deviation, median, 1st and 3rd quartiles, minimum, and maximum.
- Categorical variables will be summarized by number of participants with observed values (n), frequency counts (n1) and percent of participants with observed values.

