##### **9.4.2.1. Adverse Events**

An AE will be considered a TEAE if the AE began or worsened (increased in severity or became serious) on or after the date of the first dose of study intervention. However, an AE that occurs more than 30 days after the last dose of study intervention will not be counted as a TEAE.

An AE will be considered a treatment-emergent SAE if it is a TEAE that additionally meets any SAE criteria.

The number and percentage of participants with TEAEs during the study will be tabulated by system organ class and preferred term and by system organ class, preferred term, and severity.

The number and percentage of participants with ocular TEAEs during the study will be tabulated by preferred term.

If more than 1 AE is coded to the same preferred term for the same participant, the participant will be counted only once for that preferred term using the most severe and most related occurrence for the summarizations by severity and by relationship to study intervention.

Summary tables will be provided for participants with SAEs and participants with AEs leading to discontinuation if 5 or more participants had such events. Listings of all AEs, SAEs, and AEs leading to discontinuation by participant will be presented.

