2.3 Treatment Assignment and Blinding

Participants will be randomized to the following study intervention sequences in a 1:1 ratio:

- AGN-190584 followed by vehicle
- vehicle followed by AGN-190584

The identity of study intervention will be masked to the participants and the study center.

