4.0 Analysis Populations

The following populations are defined:

Population	Description
Intent-to-Treat (ITT)	The ITT population includes all randomized participants.
Safety	The safety population includes all treated participants who receive ≥ 1 administration of study intervention.

For analyses based on the ITT population, participants will be summarized according to the randomized study intervention. For analyses based on the Safety population, participants will be summarized according to the study intervention they actually receive in each period.

Also, only statistical analyses of safety will be performed by study period as defined in Table 4-1.

Table 4-1 Definition of the Control Period

Period	Start Date	End Date
Period 1	Date of the first dose at Visit 2	
 For participants who do not receive the treatment at Visit 4: the end date is the study exit date. For participants who receive the treatment at Visit 4: the end date is the date when the treatment is received at Visit 4 minus 1 day.
Period 2	Dose date at Visit 4	Study exit date

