9.2.3 Treatment-Emergent Adverse Events by SOC and/or PT

Treatment-emergent adverse events will be summarized by SOC and PT; by maximum relationship to study drug as assessed by the investigator (e.g., reasonable possibility or no reasonable possibility) and SOC and PT; by maximum severity and SOC and PT. Specific adverse events will be counted once for each participant for calculating percentages, unless stated otherwise. In addition, if the same adverse event occurs multiple times within a participant, the highest severity and level of relationship to investigational product will be reported.

Nonocular TEAEs will also be summarized by SOC and PT.

Ocular TEAEs will be summarized by preferred term and maximum relationship to study drug assessed by investigator.

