13.0 References

14.0 Appendices

Appendix A. Protocol Deviations

The number and percentage of subjects who reported at least one of the following protocol deviation categories will be provided.

- Subject entered the study even though s/he did not satisfy entry criteria.
- Subject developed withdrawal criteria during the study and was not withdrawn.
- Subject received wrong treatment or incorrect dose of study.
- Subject took prohibited concomitant medication.

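### SAP 9.1 fills the safety columns by randomized sequence, while SAP 4.0 requires the treatment actually received; the two differ only when a participant gets the wrong product

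*SAP*

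**What the plan says.** **Which treatment counts for safety.** SAP 4.0 has ITT analyses follow the randomized intervention. For the Safety population, "participants will be summarized according to the study intervention they actually receive in each period". It also says that safety is analyzed by study period.

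**How the safety columns are filled.** SAP 9.1 states that "The safety results will be presented by study intervention group". It then gives the rule: the AGN-190584 "group will be based on Period 1 data for study intervention sequence" AGN-190584 followed by vehicle, together with Period 2 of the reverse sequence. The vehicle column is the mirror image.

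**What a sequence is.** SAP 2.3: "Participants will be randomized to the following study intervention sequences in a 1:1 ratio". No sequence as actually taken is defined anywhere in the SAP.

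**Where else the mapping appears.** SAP 8.4 uses the same mapping for the other efficacy tables, which are ITT.

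**Wrong treatment.** Appendix A of the SAP includes the deviation category "Subject received wrong treatment or incorrect dose of study". Under protocol 6.3 and the schedule of activities, the site contacts the IxRS at Visit 2 and again at Visit 4, so each period has its own kit assignment.

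**The concern.** An as-randomized mapping sits in the section that governs as-treated tables. A programmer who follows SAP 9.1 and one who follows SAP 4.0 would place a wrongly treated participant's data in different columns, and the SAP does not say which section prevails.

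The safety tables are the trial's descriptive comparison of AGN-190584 with vehicle. If active drops are given by mistake in a vehicle period, SAP 9.1 reports reactions to them as vehicle events. If vehicle is given by mistake in an active period, SAP 9.1 adds an unexposed participant to the AGN-190584 column. For events that the drug makes more frequent, both errors tend to pull the columns together. The events of special interest in SAP 9.2.5, headache and visual disturbance, are summarized in these same columns.

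**Working it through.** **Step 1: the denominators.** SAP 2.4 gives 40 completers and 54 enrolled, and both figures reproduce.
- Take 0.11 as the within-participant variance, so the treatment difference has variance 2 × 0.11 = 0.22. With margin 0.25, one-sided 0.025 and n − 2 degrees of freedom, the noncentral t calculation reaches 90% power at n = 40 (power 90.7%).
- Dropout: 40 / (1 − 0.25) = 53.3, rounded up to 54.

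A safety column should therefore hold roughly 40 to 54 participants. That range is an assumption, since the actual number treated in each period is not known in advance.

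**Step 2: the two rules side by side.**

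| Participant | Column under SAP 4.0 | Column under SAP 9.1 |
|---|---|---|
| Planned product in both periods | Treatment taken | Same |
| Randomized to vehicle then AGN-190584, given AGN-190584 in Period 1 by error | Period 1 under AGN-190584 | Period 1 under vehicle |
| Randomized to AGN-190584 then vehicle, given vehicle in Period 1 by error | Period 1 under vehicle | Period 1 under AGN-190584 |

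Errors in Period 2 behave the same way. With no misdosing, the tables are identical.

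**Step 3: size when it happens.** Suppose one participant takes AGN-190584 in a vehicle period and has a given event in that period. Let x be the vehicle-column count under SAP 9.1, out of N.
- SAP 9.1 rate: x / N.
- SAP 4.0 rate, if this participant then has no vehicle period: (x − 1) / (N − 1).
- Difference: (N − x) / [N(N − 1)], which equals 1/N at x = 1 and is slightly less for larger x.

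At x = 1 this is 1/54 = 1.9 points or 1/40 = 2.5 points. At x = 5 it is 49/(54 × 53) = 1.7 points or 35/(40 × 39) = 2.2 points. The AGN-190584 column loses the same event (1/N), unless that participant also had it in the correctly dosed active period.

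Two or three such participants would misplace 3.7% or 5.6% of a column of 54, and 5.0% or 7.5% of a column of 40. A misdosed participant without the event changes only the denominators.

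**The case against.** **SAP 4.0 may govern.** SAP 9.1 says its analyses use the safety population, so it could be read as importing the as-received rule. It never uses the words assigned or randomized, and its bullets could be taken as explaining how two periods pool into one column. That may well be the intent, but the text does not deliver it. SAP 2.3 defines sequences only by randomization, and the mapping is the one used for ITT in SAP 8.4. Reading sequence as the order actually taken does not complete the rule either: one wrong kit means the same product in both periods, and SAP 9.1 has no entry for that.

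**It may never matter.** Kits are centrally assigned, Appendix A is only a list of categories, and nothing suggests that misdosing is expected. Safety is descriptive, protocol 9.4.2.1 provides by-participant listings of all adverse events, and wrong-treatment deviations are tabulated. All of this stands and keeps the point minor.

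**A stronger reading concerns the counting rule.** SAP 9.2.3 says "Specific adverse events will be counted once for each participant for calculating percentages, unless stated otherwise", and that "if the same adverse event occurs multiple times within a participant, the highest severity and level of relationship to investigational product will be reported". Protocol 9.4.2.1 says "the participant will be counted only once for that preferred term using the most severe and most related occurrence". None of these is limited to one intervention group, so a reader might infer that an event occurring on both treatments drops out of one column or carries its worst grade across. The documents do not support that. SAP 4.0 analyzes safety by study period, SAP 9.1 builds each column from that column's own period data, and SAP 9.2.2 gives the overview by intervention group at participant level. Counting once therefore naturally applies within each column, where nothing is lost. The protocol's statistical section describes itself as a summary, with detailed methods left to the SAP.

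**Conclusion.** The conflict between SAP 4.0 and SAP 9.1 is real on the text. As written, SAP 9.1 puts a wrongly treated participant's safety data under the treatment not taken. The effect is zero if nobody is misdosed. Otherwise it is about 1.9 points (54 in the column) to 2.5 points (40) in an event's rate, for each misdosed participant who also has that event in the affected period.

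The pull toward a smaller drug-vehicle difference is a tendency that assumes the event is more frequent on drug. A single event on wrongly given vehicle would be counted under AGN-190584 and move the other way. The documents give no misdosing frequency, so no expected bias can be stated. A reader should not infer that the safety comparison is biased as planned, or that every dispensing error shifts a rate by these amounts.

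The missing qualifier in SAP 9.2.3 is a matter of clarity, not an error.

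**What to change.** In SAP 9.1, replace the two sequence-mapping bullets with:

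> Results for each study intervention group are based on the period(s) in which the participant actually received that intervention (Section 4.0).

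Keep the sequence mapping only in SAP 8.4, where the tables are ITT. Column denominators should follow the same rule, so a participant who received one product in both periods counts once in that column and not in the other.

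As an optional clarification, SAP 9.2.3 could say that once-per-participant counting, maximum severity and maximum relationship apply within each study intervention group.

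The cost is one sentence, or two with the clarification, before database lock. It needs no new data, changes no endpoint, adds negligible programming and restates what SAP 4.0 already requires.
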